4 STUDY OBJECTIVES

To collect clinical safety and performance outcome data associated with the use of EmboCube Embolization Gelatin (EmboCube) to control bleeding or hemorrhage.

5 BACKGROUND/INTRODUCTION

This is a multicenter observational study of the use of EmboCube to control bleeding or hemorrhage. Bleeding is defined as the loss of blood from a damaged blood vessel, whereas hemorrhage is defined as massive internal or external blood loss. This study is designed to enable the collection, analysis, and reporting of data from the real-world use of EmboCube when used in accordance with the Instructions for Use (IFU) associated with its CE mark.

Data collection will include outcomes pertaining to the safety and effectiveness of EmboCube from the index procedure through 28 (0/+14) days post-procedure. Data collection will be according to the standard follow-up practices at the enrolling institutions.

5.1 STUDY DESIGN

Multicenter observational post-market clinical follow-up study in subjects treated with EmboCube to control bleeding or hemorrhage. This study does not require subjects to undergo any procedures beyond those performed under normal standard of care associated with the device.

5.2 TREATMENT GROUPS

This will be a single-arm study that will include subjects undergoing embolization with EmboCube for the treatment of bleeding or hemorrhage.

5.3 STUDY POPULATION

Subjects undergoing embolization with EmboCube for the treatment of bleeding or hemorrhage who meet the inclusion and exclusion criteria will be invited to participate in this study. The eligibility criteria are kept to a minimum to better represent the profiles of subjects treated in clinical practice without selecting sub-groups that have low or high risk or excluding subjects with certain diseases or anatomies.

5.3.1 INCLUSION CRITERIA

French Study Sites

1. Age ≥18 years
2. Subject requires embolization and is suitable for treatment with EmboCube in accordance with the device's IFU for the treatment of bleeding or hemorrhage
3. Subject provides written informed consent to participate in the study and allows for data collection

4. The subject has Social Security

Australian Study Sites

5. Age ≥ 18 years
6. Target vessel(s) that require treatment are $\leq 5\text{mm}$
7. Subject requires embolization and is suitable for treatment with EmboCube in accordance with the device's IFU for the treatment of bleeding or hemorrhage
8. Subject provides written informed consent to participate in the study and allows for data collection

5.3.2 EXCLUSION CRITERIA

French Study Sites

1. Site of bleeding is in the neck, head, or brain
2. Subject has a co-morbidity with survival prognosis < 30 days, in the opinion of the treating physician
3. In the investigator's opinion, participation in the study may not be in the subject's best interest
4. Pregnant woman, person under guardianship or curatorship, person under judicial protection, and/or person who does not write or speak French (applicable in France only)

Australian Study Sites

1. Subject's vascular anatomy precludes correct catheter placement
2. Subject's feeding arteries are too small to accept selected EmboCube
3. Bleeding site in the neck, head, or brain
4. Presence or suspicion of vasospasm
5. High-flow arteriovenous shunts with a diameter greater than the selected EmboCube
6. Use in the pulmonary vasculature
7. Use in pre-operative portal vein embolization
8. Subject has severe atherosclerosis
9. Subject has known allergy to gelatin of porcine origin
10. Subject has a co-morbidity with survival prognosis of < 30 days in the opinion of the treating physician
11. In the investigator's opinion, participation in the study may not be in the subject's best interest

5.4 INTERVENTION

EmboCube will be used in accordance with the currently approved CE mark.

EmboCube is indicated for use in the embolization of blood vessels to occlude blood flow to control bleeding/hemorrhaging in the peripheral vasculature.

5.5 SAMPLE SIZE

A minimum of 100 subjects will be included. This sample size is based on a one-sample non-inferiority analysis of clinical success based on the parameters listed below and a 15% loss-to-follow-up:

- Reference Clinical Success rate (p_0): 92%*
- Treatment rate (p): 90%
- Non-inferiority margin: 10%
- α : 0.05
- Power: 80%

*The reference Clinical Success rate is based on historical clinical literature data for benchmark gelatin embolic devices.¹⁻¹²

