PI	Principal Investigator
SADE:	Serious Adverse Device Effect
SAE:	Serious Adverse Events
UADE:	Unanticipated Adverse Device Event

PROTOCOL SUMMARY

Study Title:	A Multicenter Observational Study to Evaluate Outcomes of EmboCube Gelatin Embolization to Control Bleeding or Hemorrhage
Study Objective:	To collect clinical safety and performance outcome data associated with the use of EmboCube Embolization Gelatin to control bleeding or hemorrhage.
Study Device:	EmboCube Embolization Gelatin
Study Design:	Multicenter observational post-market clinical follow-up study in subjects treated with EmboCube
Device Regulatory Status:	CE mark approved March 2019 (CE 667862).
Sample size:	
A minimum of 100 subjects will be included. This sample size is based on a one-sample non-inferiority analysis of Clinical Success based on the parameters listed below and a 15% loss-to-follow-up:
 
 • Reference Clinical Success rate (p_0): 92% • Treatment rate (p): 90% • Non-inferiority margin: 10% • α: 0.05 • Power: 80% 
The reference Clinical Success rate is based on historical clinical literature data for benchmark gelatin embolic devices.

Subject Population:	Subjects who are treated with EmboCube to control bleeding or hemorrhage in accordance with the current approved CE Mark indication for use as stated in the Instructions for Use (IFU).
Clinical Sites:	Up to 7 centers may be included to allow enrollment of required subjects.
Study Follow-Up:	Data will be collected to 28 days post procedure.
Estimated Study Duration:	
First patient enrolled: July 2022
 
Last patient enrolled: July 2023
 
Last patient, last visit: August 2023

Primary Endpoints:	
The primary performance endpoint will be clinical success defined as cessation of bleeding post-embolization and absence of rebleeding at the treated site requiring reintervention (repeat embolization or additional surgery) within 24 hours.
 
The primary safety endpoint will be absence of unanticipated serious adverse device effects within 24 hours.

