9 STATISTICAL ANALYSIS

The analysis of the data from this study will be primarily descriptive. Continuous endpoints will be summarized by N, mean, standard deviation, median, minimum, and maximum. Categorical or binary endpoints will be summarized by N and percentage with confidence intervals as appropriate. Kaplan Meier plots will be used to display and summarize time to event data.

The planned sample size for analysis is at least 100 subjects which is believed to be adequate to provide an accurate characterization of EmboCube in a "real-world" clinical setting.

Analysis Population

- *Intention-to-Treat (ITT) Analysis Set:* includes all enrolled subjects.
- *Per-Protocol (PP) Analysis Set:* includes all enrolled subjects who met all inclusion/exclusion criteria with no major protocol deviations. This is a secondary analysis set for the primary safety and effectiveness endpoints, as well as secondary endpoints.

While ITT is intended as the primary analysis set for all safety and effectiveness endpoints, the primary safety and effectiveness endpoints will additionally be evaluated in the PP analysis sets as supportive information. All subjects excluded from ITT analysis set will be described.

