9.2 Primary Endpoint Analysis

Endpoints will be analyzed using the intention-to-treat analysis set. An additional supportive analysis will be conducted in the PP analysis sets for the primary safety and effectiveness endpoints. All available data will be used for each endpoint and no imputations will be done.

The primary endpoint of clinical success will be presented as frequency and percentage.

The primary safety endpoint of absence of SADE within 24 hours, will be presented as frequency and percentage.

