9.4 Sample Size

The sample size of 100 subjects is based on a one-sample non-inferiority analysis of Clinical Success based on the parameters listed below and a 15% loss-to-follow-up:

- Reference Clinical Success rate (p_0): 92%

- Treatment rate (p): 90%
- Non-inferiority margin: 10%
- α : 0.05
- Power: 80%

The reference Clinical Success rate is based on historical clinical literature data for benchmark gelatin embolic devices.

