8 STATISTICAL METHODOLOGY

8.1 GENERAL METHODOLOGY

Final analyses will be performed after all study subjects have completed the final follow-up visit, defined according to the protocol as 28 (0/+14) days.

For continuous variables, outputs will be presented with mean, standard deviation (SD), median, minimum, and maximum values. Mean and median values will be rounded to a single decimal place while SD will be rounded to two decimal places. When appropriate, a corresponding 95% confidence interval (CI) will be calculated. Categorical variables (e.g., sex, race) will be reported using frequencies and percentages. All percentages will be rounded to one decimal place. If percentages do not add up to 100% due to rounding, a footnote explanation will be provided accordingly.

When the mean is not an appropriate measure of central tendency, alternative statistics will be considered (e.g., median). When the distribution of a variable does not support the use of parametric statistics, nonparametric approaches or data transformations may be implemented. If data transformations are used, they will be specified in the final clinical report.

Correlation analyses will be used to analyze relationships for continuous variables. Independent t-tests will be conducted to test differences for continuous variables between binary groups. A Fisher's exact test will be used to analyze the relationships between categorical variables. P-values less than or equal to 0.05 will be considered significant. All p-values will be rounded to 3 decimal places and will be presented as "<0.001" if less than 0.0005.

Time-dependent response variables will be expressed using the Kaplan-Meier curve, and the hazard ratio and the 95% CI will be reported.

Data for all categorical endpoints are shown with the number of patients, percentage, and Clopper-Pearson's exact 95% CI.

Descriptive statistics will be used to examine demographic and baseline characteristics and to perform other efficacy analyses.

Each table generated will have headers that include the total sample size (N). Frequencies and percentages for categorical variables will be calculated using the number of subjects (n) with non-missing values.

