8.1.5 INTERIM ANALYSIS

Interim analyses will be performed to support regulatory submission(s) and as needed to support conferences, presentations, or publications. No pre-stated study stopping rules are planned.

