8.2 PRIMARY DATA ANALYSES

Endpoints will be analyzed using the ITT analysis set. Additional supportive analyses will be conducted in the PP analysis sets for the primary safety and effectiveness endpoints. All available data will be used for each endpoint and no imputations of data are planned.

The primary endpoint of clinical success (defined as cessation of bleeding post-embolization and absence of re-bleeding at the treated site requiring re-intervention [i.e., repeat embolization or additional surgery], within 24 hours) will be presented as frequency and percentage.

Endpoint Derivation:

- “Was there a re-intervention to treat bleeding?” is checked NO, **AND**
- “Was occlusion of the treated area (as seen on post-embolization angiogram) successful?” is checked YES, **AND**
- “Did subject have any re-interventions post-procedure through 24 hours post-procedure?” is checked NO

The primary safety endpoint of absence of serious adverse device effect within 24 hours will be presented as frequency and percentage

Endpoint Derivation:

- “Did any serious and device- and/or procedure-related adverse events occur during the procedure or up to 24 hours post-procedure?” is checked NO

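### The sample size claims 80% power for a non-inferiority analysis that no section performs; by an exact method against the implied 82% floor, power would be below 80% at 85 to 100 subjects

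*SAP*

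**What the plan says.** Four places give the same basis for the number of subjects: SAP 5.5, the SAP synopsis, Protocol 9.4 and the Protocol Summary. SAP 5.5 reads "This sample size is based on a one-sample non-inferiority analysis of clinical success based on the parameters listed below and a 15% loss-to-follow-up", and Protocol 9.4 reads "The sample size of 100 subjects is based on a one-sample non-inferiority analysis of Clinical Success based on the parameters listed below". The parameters are a reference rate of 92%, a treatment rate of 90%, a margin of 10%, alpha 0.05 and power 80%. The minimum enrolment is 100.

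The analysis sections describe something else:

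- Protocol 9: "The analysis of the data from this study will be primarily descriptive".
- Protocol 9.2: "The primary endpoint of clinical success will be presented as frequency and percentage". SAP 8.2 says the same of clinical success: "within 24 hours) will be presented as frequency and percentage".
- SAP 8.1 adds an interval: "Data for all categorical endpoints are shown with the number of patients, percentage, and Clopper-Pearson's exact 95% CI". It is not compared with any value.
- SAP 9.1 lists no table with a non-inferiority result.
- On interim looks, SAP 8.1.5 says: "Interim analyses will be performed to support regulatory submission(s) and as needed to support conferences, presentations, or publications". Protocol 9.6 is similar.

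**The concern.** A power figure is a property of a specified test. Here the test is missing: there is no null hypothesis, no stated floor (92% less 10 points is 82%, but neither document says so), no sidedness for alpha and no rule for concluding non-inferiority. The t-tests, Fisher tests and correlations in SAP 8.1 compare groups or variables, not a rate with a reference.

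This matters because results are meant for regulatory submissions, where they would appear beside a non-inferiority, 80% power label. If someone then judges non-inferiority, the rule can be chosen after the data are seen, and near the floor that choice can decide the answer. The 80% is also not the power of the only interval method the SAP names, which is exact.

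**Working it through.** **Inputs** (SAP 5.5, Protocol 9.4): reference 0.92, margin 0.10 (read as absolute), true rate 0.90, alpha 0.05, power 0.80, loss 15%, N = 100. Implied floor: 0.92 − 0.10 = 0.82. Distance from the true rate: 0.90 − 0.82 = 0.08. Evaluable after the stated loss: 100 × 0.85 = 85.

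**Reproducing the plan's figure.** Normal approximation, one-sided 5%, variance at 0.90:

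n = 0.90 × 0.10 × ((1.645 + 0.842)/0.08)² = 86.9, so 87.

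Allowing for loss, 87/0.85 gives 103 and 87 × 1.15 gives 101, both close to 100. Formula power at 85 is Φ(√85 × 0.08/0.30 − 1.645) = 79.2%, so the small shortfall from 87 to 85 is immaterial. The other variants tried do not give about 87: 122.2 with the null variance in the alpha term, 114.1 with the arcsine method, and 110.4 at one-sided 2.5% with the variance at 0.90. The stated N thus rests on one formula that the documents do not name.

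**Actual power of three possible rules.** For each rule, take the smallest number of successes whose lower bound exceeds 82%. Then compute the binomial probability of reaching it at 0.90 (power) and at 0.82 (type I error).

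| Rule | Successes needed at 85 / 100 | Power at 85 / 100 | Power range, n = 85 to 100 | Type I error at 85 / 100 |
|---|---|---|---|---|
| One-sided 5% Wald | 75 / 88 | 77.2% / 80.2% | 72–83% | 8.3% / 7.1% |
| One-sided 5% exact | 76 / 89 | 65.7% / 70.3% | 59–73% | 4.4% / 3.9% |
| Lower limit of the planned exact 95% interval | 77 / 90 | 52.0% / 58.3% | 45–61% | 2.1% / 2.0% |

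Exact power moves in a saw-tooth with n, hence the ranges. Neither exact rule reaches 80% at any n from 85 to 100. The Wald rule does reach 80% at 100, but with a true type I error above the stated 5% (5.7% to 9.4% over the range).

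**How often the choice of rule would matter, at n = 100.**

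- 88 successes: the Wald bound is 82.7% (pass) and the one-sided exact bound is 81.3% (fail).
- 89 successes: the one-sided exact bound is 82.4% (pass) and the lower limit of the planned 95% interval is 81.2% (fail).
- At a true rate of 90%, P(88) + P(89) = 9.9% + 12.0% = 21.9%.

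**Interim looks.** Suppose a one-sided 5% exact test were added and also applied unadjusted at interims. Type I error would rise from 3.9% (at 100 only) to 6.5% (at 50 and 100) or 8.5% (at 33, 67 and 100). The look times are assumptions, since the documents give none.

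**The case against.** The best reply is that nothing was miscalculated. The 80% is right for the formula behind it, and the matching Wald rule has an actual power of 80.2% at 100. The exact interval in SAP 8.1 is a way of displaying results, not a decision rule, so the lower power figures belong to tests that the plan does not contain. The study is observational, has no success criterion or stopping rule, and aims to collect outcome data. Protocol 9 also gives a separate, qualitative reason for 100 subjects: that they should characterise the device adequately in routine use. On this view harm arises only if someone later declares non-inferiority, and the interim figures describe a hypothetical design.

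Much of this is fair. The N is not an arithmetic slip, the exact power figures are conditional, and the interim figures rest on assumed looks. What remains is that four places claim power for an analysis that is not planned. If the study is purely descriptive, that is a reason to remove the claim. The Wald reading does not rescue it either: it delivers the stated 80% at 100 only with a type I error of 7.1% against the stated 5%. Because 100 is a minimum, larger enrolment would raise power, but the documents claim 80% at the minimum.

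**Conclusion.** The concern holds. The claimed 80% power is a property that the planned analysis does not have, because that analysis contains no test. This part rests on the text alone.

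The size of the power gap is conditional on judging non-inferiority against 82% (an absolute margin) at a true rate of 90%. At 100 evaluable subjects, power would then be 70% with a one-sided 5% exact bound and 58% with the planned 95% interval. At 85 the figures are 66% and 52%. The values at 100 are the more relevant, because the endpoint is read at 24 hours in subjects already treated, so few should be lost. The text should be corrected before any result is reported, since a rule chosen later is no longer pre-specified.

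**What to change.** **(a) Preferred, as it fits a study declared mainly descriptive.** In SAP 5.5, Protocol 9.4 and both synopses, delete the non-inferiority parameters and the power claim. Justify 100 subjects by the precision of the exact 95% interval already planned: 80/100 gives 70.8% to 87.3%, 90/100 gives 82.4% to 95.1%, and 95/100 gives 88.7% to 98.4%. This changes wording only; the price is losing the power claim.

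**(b) If a non-inferiority conclusion is wanted.** In SAP 8.2 and Protocol 9.2, state H0: p ≤ 0.82 against H1: p > 0.82, decided by the exact lower bound, and give the one-sided alpha. Say that the test is done once, at the final analysis, and that the interim analyses in SAP 8.1.5 and Protocol 9.6 are descriptive only. Restate power for that rule over 85 to 100 evaluable subjects: about 59–73% at one-sided 5%, or 45–61% at one-sided 2.5%. This costs wording and one line of analysis, with no added patients, but the stated power is less favourable. If 80% exact power were wanted at one-sided 5%, it is first reached at 118 evaluable subjects and holds for every n from 138.

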5.6 STUDY PROCEDURE

It is anticipated that enrollment will commence in July 2022 and is expected to continue until July 2023. The last subject visit is expected in August 2023.

Subject follow-up visits will be in accordance with standard of care. Data will be collected from available medical records for baseline (medical history), index hospitalization, up to 24 hours post-procedure, and until 28 days post-procedure. If there is no routine clinic visit or follow-up between 4 and 6 weeks post-procedure (28 [0/+14] days), subjects will be contacted by telephone during this time to collect safety follow-up data to 28 days.

Start of the study will be defined as the date of initiation (i.e., authorization to start enrollment) of the first site.

Study completion will be defined as the completion of the last follow-up visit/contact for the last subject.

5.7 VISIT SCHEDULE

Study participation will last for a total of 28 (0/+14) days (i.e., 28 to 42 days). Follow-up will be by clinic visit or telephone according to site standard of care. Data will be collected from available medical records for baseline, index hospitalization, and standard of care follow-up until 28 days post-procedure. If there is no routine clinic visit or follow-up between 4 and 6 weeks post-procedure (28 [0/+14] days) subjects will be contacted by telephone during this time to collect safety follow-up data to 28 days.

A summary schedule of the data collection for tests and evaluations is provided in Table 1. Data from tests and evaluations performed outside of standard of care will not be collected.

Table 1. Data Collection Schedule

Data	Pre-operative/ baseline	Procedure to 24 hours	28 (0/+14) days follow-up ¹
Informed consent ²	X		
Demographics	X		
Diagnosis (i.e., cause and location of bleeding or hemorrhage)	X	X	
Procedural information		X	
Clinical Success		X	
Technical success		X	
EmboCube use (i.e., size, type, and amount)		X	

Data	Pre-operative/ baseline	Procedure to 24 hours	28 (0/+14) days follow-up ¹
No/type of other adjuvant embolic employed		X	
Device- and/or procedure-related serious adverse events		X	X
Occurrence of re-intervention to control bleeding at the treated site		X	X
Concomitant antiplatelet and anticoagulant medications	X	X	X

¹If a subject does not have a clinic visit at the site between 4 and 6 weeks (i.e., 28 to 42 days), the subject will be telephoned to collect information on potential device-related adverse events and re-interventions.

²Subject will be asked to provide written informed consent for data collection either pre-operatively or prior to hospital discharge.

6 ANALYSIS POPULATION

The following analysis populations are identified for the study:

- Intention-to-Treat (ITT) analysis set: includes all enrolled subjects.
- Per-Protocol (PP) analysis set: includes all enrolled subjects who meet all inclusion/exclusion criteria with no major protocol deviations. This is a secondary analysis set for the primary safety and effectiveness endpoints, as well as secondary endpoints.

While the ITT analysis set is intended as the primary analysis set for all safety and effectiveness endpoints, the primary safety and effectiveness endpoints will also be evaluated in the PP analysis set as supportive information. All subjects excluded from the ITT analysis set will be described.

7 OUTCOME VARIABLES

7.1 PRIMARY OUTCOMES

7.1.1 PRIMARY EFFECTIVENESS ENDPOINT

The primary performance endpoint will be clinical success defined as cessation of bleeding post-embolization and absence of re-bleeding at the treated site requiring re-intervention (i.e., repeat embolization or additional surgery) within 24 hours.

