4 ENDPOINTS AND SUBJECT POPULATION

4.1 Primary Outcome Measures

4.1.1 Primary effectiveness endpoint

The primary performance endpoint will be clinical success defined as cessation of bleeding post-embolization and absence of rebleeding at the treated site requiring reintervention (repeat embolization or additional surgery), within 24 hours.

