6.3 Procedural Information

All procedures should be conducted in accordance with site standard of care and patient needs, there are no prohibited concomitant treatments. EmboCube Embolization Gelatin shall be used in accordance with the IFU.

Data collected will include the following:

- Procedure type
- Treated vessel and treated area
- Occlusion of the target area as seen on post-embolization angiography
- Time to hemostasis (TTH) post-EmboCube embolization
- EmboCube Embolization Gelatin size, type and number of units used
- Additional embolic agents used in procedure (e.g., coils, glue, microspheres) - number and type and whether used pre- or post EmboCube
- Transfusion/ use of blood products
- Coagulation status (PT, PTT, INR)
- Repeat embolization or additional surgery to address bleeding within 24 hours
 - Rebleeding due to treated vessel
- Serious and device and/or procedure related adverse events
- Device observations – any observations relating to handling and delivery of EmboCube
- Concomitant anticoagulants and antiplatelet medications

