6.4 Follow-Up

The following data will be collected by review of all medical records available for the period between index procedure and 28 days. In the event the subject is not seen for routine clinic visit or follow-up between 4- and 6-weeks post procedure (28 days +14 days), subjects will be contacted by telephone during this time to confirm their current status and collect safety information.

- Date of discharge post-index procedure
- Concomitant anticoagulants and antiplatelet medications
- Number, type, and timing of additional interventions to treat bleeding
 - Rebleeding due to treated vessel
- Serious and device and/or index procedure related adverse events

Subjects will continue to be treated according to standard routine practice after completion of study.

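### The clinical success definition fails only treated-site re-bleeding needing repeat embolization or surgery, but the SAP 8.2 derivation fails any re-intervention, so one subject can be scored both ways

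*SAP*

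**What the plan says.** **Definition.** SAP 7.1.1 makes success depend on two parts. The first is "clinical success defined as cessation of bleeding post-embolization" and the second is "absence of re-bleeding at the treated site requiring re-intervention (i.e., repeat embolization or additional surgery) within 24 hours". Protocol 4.1.1 has the same second part: "absence of rebleeding at the treated site requiring reintervention (repeat embolization or additional surgery), within 24 hours". SAP 8.2 repeats the definition before giving its derivation.

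**Derivation.** SAP 8.2 scores a success when three form items are answered as required. "Was there a re-intervention to treat bleeding" must be NO, angiographic occlusion of the treated area must be YES, and "Did subject have any re-interventions post-procedure through 24 hours post-procedure" must be NO.

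**Data collection.** Among the procedural data, Protocol 6.3 lists "Repeat embolization or additional surgery to address bleeding within 24 hours". For the period from the index procedure to day 28, Protocol 6.4 lists "Number, type, and timing of additional interventions to treat bleeding". Both sections carry a sub-item on whether the re-bleeding came from the treated vessel. Table 1 in both documents records re-intervention for bleeding at the treated site, in the 24-hour and 28-day columns, without a type limit.

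**The concern.** The SAP definition closes its list of failing re-interventions at two types. The items that produce the analysed variable do not use that list. If the two differ for some subjects, the reported rate is not the rate of the endpoint as defined, and a reader of the report cannot tell which one it is.

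The study can pool up to 7 centers and deliberately takes varied causes and anatomies, including uterus and viscera. It is plausible, though the documents give no frequency, that some re-bleeds are controlled by means other than a second embolization or an operation. If sites understand re-intervention differently, they feed different endpoints into one percentage.

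**Working it through.** No figure in the plan is in dispute, so the main check is a comparison of texts.

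**Step 1: conditions for failure on the re-intervention part**

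| Source | Type limited to two? | Treated site required? | For bleeding? | 24-hour window? |
|---|---|---|---|---|
| Definition (Protocol 4.1.1, SAP 7.1.1) | Yes | Yes | Yes | Yes |
| SAP 8.2, first item | No | No | Yes | Not in its wording |
| SAP 8.2, last item | No | No | No | Yes |
| Protocol 6.3 list | Yes | Sub-item on treated vessel | Yes | Yes |
| Protocol 6.4 list | No | Sub-item on treated vessel | Yes | Timing recorded |
| Table 1 (both documents) | No | Yes | Yes | 24-hour column |

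**Step 2: apply definition and derivation to the same subject.** Take a subject whose bleeding stopped after embolization and whose occlusion item is YES. The events below fall within 24 hours.

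| Event | By definition | By SAP 8.2, items read literally |
|---|---|---|
| Treated-site re-bleed, repeat embolization or surgery | Failure | Failure |
| Treated-site re-bleed, intervention of another type | Success | Failure |
| Re-intervention for bleeding elsewhere | Success | Failure |
| Re-intervention not for bleeding | Success | Failure (last item) |
| Re-bleed managed without anything ticked as a re-intervention | Success | Success |

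Three of the five rows disagree. In the second row the score also depends on the site: one that takes re-intervention in the two-type sense of "requiring reintervention (repeat embolization or additional surgery), within 24 hours" answers NO, and the subject is a success.

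**Step 3: direction.** Measured against the two-type definition, the re-intervention items read literally can only lower the rate. Measured against an any-type rule, two-type answers by sites can only raise it. The derivation also has no item for cessation of bleeding and uses angiographic occlusion instead, which can err either way. The documents do not say how sites answer, so the net direction is open.

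**Step 4: size per subject.** One subject scored differently moves the rate by 1/100 = 1.0 point with 100 analysed, or 1/85 = 1.2 points with 85 (100 × 0.85, after the plan's 15% loss).

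For context, the sample size follows from n = p(1 − p)(z_α + z_β)² / (p − limit)², with p = 0.90, limit = 0.92 − 0.10 = 0.82, one-sided α = 0.05 (the sidedness is not stated; this choice comes close to the plan's figure) and power 80%:

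0.09 × (1.6449 + 0.8416)² / 0.08² = 86.94, so 87; 87 × 1.15 = 100.05, or 87/0.85 = 102.4, so 103.

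The plan's 100 is thus reproduced approximately, and this point does not challenge it.

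If the observed rate happened to be at the planning value (an assumption), the exact 95% intervals would be:

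- 89/100: 81.2 to 94.4
- 90/100: 82.4 to 95.1
- 91/100: 83.6 to 95.8

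One subject can then decide on which side of 82% the lower limit falls. That mainly reflects a starting point 0.4 points above 82%, and it is not a forecast.

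**The case against.** The strongest objection concerns a reading that the definition invites. A reader might infer that re-bleeding treated by any other means is scored as success, and that the success rate is therefore inflated. SAP 8.2 does not support this. Its items carry no type limit, so a re-intervention of another type that is ticked on the form is a failure. On this part the derivation is stricter than the definition. That objection stands, and inflation is not claimed here.

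Three further objections have weight:

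- The form and its completion guidance are not in the documents and may define re-intervention. Nor is additional surgery defined, so some other techniques might fall under it. This limits how sure one can be that sites will differ, but it does not remove the mismatch inside SAP 8.2, which states the two-type definition and then an untyped derivation.
- The analysis is described as primarily descriptive, the primary result is a frequency and percentage, and no test against 82% is stated. The intervals above therefore show sensitivity only.
- Re-intervention tables and listings are already planned. They describe the procedures, but they neither say which ones count as failure nor give the alternative rate.

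**Conclusion.** The point holds as a mismatch between definition and derivation. The definition fails a subject only for treated-site re-bleeding needing one of two re-interventions within 24 hours. SAP 8.2 fails a subject for any re-intervention, and its last item has no treated-site or bleeding condition. The collection lists do not settle the matter, because Protocol 6.3 names the two types and Protocol 6.4 and Table 1 do not.

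The size is 1 point per affected subject in 100. The number of such subjects and the net direction cannot be derived from the documents, and no estimate is offered. The conclusion rests on the form items as quoted in SAP 8.2; a definition of re-intervention on the form itself could narrow the gap. The primary endpoint should have one scoring rule before analysis, so the change is worth making although its effect is unknown.

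**What to change.** 1. In SAP 8.2, make the re-intervention part of the derivation match the stated definition. Classify each re-intervention within 24 hours by the type, timing and treated-vessel information recorded under Protocol 6.4, and state that the treated-vessel answer is what identifies the treated site.
2. Instruct sites to record every re-intervention for bleeding whatever its type, so that the classification is made once, centrally, and not by each site when it answers the form.
3. Beside the primary rate, report one supportive row in which any re-intervention for bleeding at the treated site within 24 hours, of any type, counts as failure. Give it the Clopper-Pearson 95% interval that SAP 8.1 already prescribes.

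The cost is one SAP paragraph, one site instruction and one table row. Protocol 6.4 already provides for the data. The downside is a second success figure, equal to the aligned primary rate or slightly lower. Aligning the derivation may also give an equal or higher primary rate than the current items read literally; the supportive row makes the part due to intervention type visible.
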